2.2.3 Supportive Efficacy Endpoints/Variables

2.2.3.1 Other Remission and Response Endpoints/Variables

- Proportion of subjects in remission from week 16 through week 52, where remission is defined as maintaining CDAI score < 150 from week 16 through week 52. Subjects experiencing a CDAI score ≥ 150 at any visit time point assessment between week 16 and week 52 or have no CDAI measurement at week 16 or week 52 will be considered not achieved Remission for this endpoint analysis.
- Proportion of subjects experienced early response week 16, where early response is defined as reduction from baseline of ≥ 100 in CDAI score. Subjects who have a change from baseline to week 16 in CDAI score which is not a reduction of ≥ 100 or who do not have a change from baseline to week 16 in CDAI score will be classified as not experienced early response.
- Proportion of subjects experienced response week 52, where response is defined as reduction from baseline of ≥ 100 in CDAI score. Subjects who have a change from baseline to week 52 in CDAI score which is not a reduction of ≥ 100 or who do not have a change from baseline to week 52 in CDAI score will be classified as not experienced response.

2.2.3.2 Time to Event Endpoints/Variables

- Time to remission – Number of weeks after randomization that a subject first records a state of remission (CDAI score < 150). It will be calculated as the date on which remission is first observed minus the date of the baseline visit (Visit 1), plus 1 day, divided by 7. For subjects still on study and not achieved remission at the time of

assessment, time to remission will be censored at the date of the last assessment of CDAI score.

- Duration of remission – Duration of remission defined as the number of weeks the subject is in remission (CDAI score < 150). It will be calculated as the first date following remission at which CDAI is ≥ 150 minus the date of remission, plus 1 day, divided by 7. Those subjects who experienced remission and continue to be in remission at the time of their last CDAI assessment will be censored at the date of their last CDAI assessment. Duration of remission will be calculated only for patients achieving remission.
- Time to response – Number of weeks after baseline that a subject first achieves a state of response (a reduction from baseline of ≥ 100 in CDAI score). It will be calculated as the date on which response is first observed minus the date of the baseline visit (Visit 1), plus 1 day, divided by 7. For those subjects not experienced response, time to response will be censored at the date of the last assessment of CDAI score.
- Duration of response – Defined as time in weeks that a subject is in a state of response (a reduction from baseline of ≥ 100 in CDAI score). It will be calculated as the first date following response at which the reduction from baseline in CDAI is < 100 minus the date of response, plus 1 day, divided by 7. Those subjects who experienced response and continue to be in response at the time of their last CDAI assessment will be censored at the date of their last CDAI assessment. Duration of response will be calculated only for patients achieved response.

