2.2.1 Primary Efficacy Endpoint/Variable: Remission

In general use of rescue medication is considered as treatment failure (not achieve remission or response) if there are any new use of rescue medication to treat CD or increased rescue medication dose from baseline prior to any remission or response assessment. Please refer to section 6.1.8 for more details.

The primary efficacy variable is the proportion of subjects experienced remission at Week 26, where remission is defined as a subject having a Crohn's Disease Activity Index (CDAI) score of <150 . Subjects who have a Week 26 CDAI measurement ≥ 150 or who do not have a CDAI measurement at Week 26 will be classified as not achieved remission.

The CDAI is used to assess the activity of CD; higher scores indicate more active disease.

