6.1.8 Efficacy Data with High Doses of Steroids Use and Rescue Medications Use

Corticosteroids Use:

A subject may use corticosteroids or increased dose levels of corticosteroids for reasons other than CD, and may start corticosteroid tapering at 8 weeks. If the subject experiences a worsening of disease activity during the taper, and/or the oral corticosteroid dose temporarily increased, in these circumstances the subject will be considered a treatment failure in the steroid free remission analysis but will continue to remain on the study and complete all scheduled visits.

Use of Rescue Medications:

Final Version 3.0, 05 April 2018

Subjects rescued with the following treatments or whose baseline doses/regimens are increased to treat new or unresolved CD symptoms may remain on the study drug at the discretion of the investigator and continue to be assessed at all scheduled study visits:

- Oral or rectal 5-ASA compounds
- Azathioprine or 6-mercaptopurine (6-MP) or methotrexate
- Antibiotics as treatment of CD
- Total parenteral nutrition as treatment of CD
- Systemic or rectal corticosteroid therapy
- Anti-TNF or other biologic agent

In the ITT efficacy analyses, subjects who initiate or modify dose/regimens to treat CD symptoms will be considered as treatment failures.

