Table 14.2.2.3.3	Sensitivity Analysis – Durable Remission Week 26 through Week 52: Per-protocol Population
Table 14.2.2.3.4	Sensitivity Analysis - Durable Remission Week 26 through Week 52: Completers Analysis (Observed Cases)
Table 14.2.2.3.5	Exploratory: Durable Remission Week 26 through Week 52 by Treatment Group for Each Baseline Subgroup from Logistic Regression analysis: Intent-to-Treat Population
Figure 14.2.2.3.1	Exploratory: Durable Remission Week 26 through Week 52 Forest Plots by Treatment Group for Each Baseline Subgroup Analysis: Intent-to-Treat Population
Table 14.2.2.4.1	Early Remission Week 16: Intent-to-Treat Population
Table 14.2.2.4.2	Sensitivity Analysis – Early Remission Week 16: Modified Intent-to-Treat Population
Table 14.2.2.4.3	Sensitivity Analysis - Early Remission Week 16: Per-protocol Population
Table 14.2.2.4.4	Sensitivity Analysis - Early Remission Week 16: Completers Analysis (Observed Cases)
Table 14.2.2.4.5	Exploratory: Early Remission Week 16 by Treatment Group for Each Baseline Subgroup from Logistic Regression analysis: Intent-to-Treat Population
Figure 14.2.2.4.1	Exploratory: Early Remission Week 16 Forest Plots by Treatment Group for Each Baseline Subgroup Analysis: Intent-to-Treat Population
Table 14.2.2.5.1	Steroid Free Remission Week 52: Intent-to-Treat
Table 14.2.2.5.2	Sensitivity Analysis – Steroid Free Remission Week 52: Modified Intent-to-Treat Population
Table 14.2.2.5.3	Sensitivity Analysis - Steroid Free Remission Week 52: Per-protocol Population
Table 14.2.2.5.4	Sensitivity Analysis - Steroid Free Remission Week 52: Completers Analysis
Table 14.2.2.5.5	Exploratory: Steroid Free Remission Week 52 by Treatment Group for Each Baseline Subgroup from Logistic Regression analysis: Intent-to-Treat Population
Figure 14.2.2.5.1	Exploratory: Steroid Free Remission Week 52 Forest Plots by Treatment Group for Each Baseline Subgroup Analysis: Intent-to-Treat Population
Supportive/Supplementary Endpoints: Time-to-Event Endpoints	
Table 14.2.3.1.1	Time to Remission: Intent-to-Treat Population
Table 14.2.3.1.2	Duration of Remission: Intent-to-Treat Population
Table 14.2.3.1.3	Time to Response: Intent-to-Treat Population
Table 14.2.3.1.4	Duration of Response: Intent-to-Treat Population
Figure 14.2.3.1.1	Time to Remission Kaplan Meir Survival Curve: Intent-to-Treat Population
Figure 14.2.3.1.2	Duration of Remission Kaplan Meir Survival Curve: Intent-to-Treat Population

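### Duration of remission and of response (SAP 2.2.3.2) ends only on CDAI, so a remission or response kept after rescue for Crohn's disease counts as ongoing, against the SAP's own rule that rescue is failure

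*SAP*

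**What the plan says.** SAP 2.2.3.2 defines four time-to-event endpoints, all by CDAI thresholds and dates.

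- Duration of remission is "the first date following remission at which CDAI is ≥ 150 minus the date of remission", plus one day, divided by 7. On censoring: "Those subjects who experienced remission and continue to be in remission at the time of their last CDAI assessment will be censored". The censoring date is the day of that assessment. Only subjects who achieve remission contribute.
- Duration of response has the same form, with "the first date following response at which the reduction from baseline in CDAI is < 100 minus the date of response".
- Time to remission and time to response run to the first CDAI below 150, or the first fall of at least 100, and are otherwise censored at the last CDAI.

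SAP 6.3.3.1 (Cox model, log-rank test, Kaplan-Meier) adds no rescue clause. It censors at the last visit, or at last contact for early discontinuations.

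Rescue is covered elsewhere. SAP 2.2.1 opens with a general rule, "In general use of rescue medication is considered as treatment failure (not achieve remission or response"), which applies when new or increased rescue for Crohn's disease precedes any such assessment. SAP 6.1.8 lists the rescue treatments, including anti-TNF or other biologics and systemic or rectal corticosteroids, and says that rescued subjects "may remain on the study drug at the discretion of the investigator and continue to be assessed at all scheduled study visits". It then states: "In the ITT efficacy analyses, subjects who initiate or modify dose/regimens to treat CD symptoms will be considered as treatment failures". The four endpoints are listed in 8.1 as ITT tables, for example "Duration of Remission: Intent-to-Treat Population".

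**The concern.** Because rescued subjects stay under observation, CDAI values after rescue will exist and will enter any derivation that looks only at CDAI. The duration formula does exactly that. A subject who starts a new biologic while in remission, and stays below 150, goes on accruing remission time in the randomised arm although the SAP regards that subject as a failure from rescue onward.

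Duration would then measure study drug plus rescue, while the remission and response proportions in the same report measure study drug without rescue. The endpoint is supportive, but it carries a p-value. The protocol and SAP also give longer time in response or remission as one of the reasons for following subjects on randomised treatment to Week 52. If the handling is left open, it may be settled after unblinding.

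**Working it through.** The SAP states no expected duration, hazard ratio or event count for these endpoints, so there is no figure of the plan's to reproduce. The check sets the rules side by side and applies the SAP's own formula.

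**1. One subject, duration of remission (hypothetical).** In remission at Week 12 (Day 85), rescue started at Week 18 (Day 127), CDAI below 150 at every visit to Week 52 (Day 365).

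| Rule applied | Arithmetic | Result |
|---|---|---|
| 2.2.3.2 as written | (365 − 85 + 1)/7 = 281/7 | 40.1 weeks, censored |
| Rescue ends the remission | (127 − 85 + 1)/7 = 43/7 | 6.1 weeks, event |
| 6.1.8 read without time order (failure throughout) | no remission achieved | not in the duration analysis |

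A second example points the same way. With remission at Week 16, rescue at Week 26 and CDAI below 150 to Week 52, the formula gives (252 + 1)/7 = 36.1 weeks, censored. Counting rescue as the end gives (70 + 1)/7 = 10.1 weeks, as an event.

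**2. Does the general rule supply the missing end date?** It does not. Section 2.2.1 classifies an assessment as achieved or not achieved. If every assessment after rescue is treated as not in remission, the first subject above no longer fits the censoring clause, which requires remission at the last CDAI. That subject does not meet the end-date clause either, because CDAI never reaches 150. The only branch that gives a number is the CDAI-only one.

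**3. Time to remission or response.** Here 2.2.1 does most of the work: rescue before the assessment means not achieved. What is missing is the date to use. The text does not say whether such a subject is censored at rescue, censored at the last CDAI or visit, or kept event-free to the end of follow-up.

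**4. How much could that choice matter?** The documents give no rescue rates, so the following rests on assumptions: 36% and 21% remitting without rescue (the Week 26 design rates, reused here) and 40% of rescued subjects reaching CDAI below 150.

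- 15% of active and 30% of placebo non-remitters rescued, post-rescue remissions counted: active 0.36 + 0.64 × 0.15 × 0.40 = 39.8%; placebo 0.21 + 0.79 × 0.30 × 0.40 = 30.5%. The difference is 9.4 points instead of 15.
- 20% rescued in both arms: 41.1% and 27.3%, a difference of 13.8 points.

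A Cox simulation on the CDAI visit schedule assumed the same Week 26 rates and that rescue multiplies the remission hazard by 2 to 3. With rescue by Week 26 in 20% versus 10%, or 30% versus 15%, of placebo versus active, the hazard ratio was 1.55–1.69 on CDAI alone. It was 2.05–2.23 with rescue as failure and subjects carried event-free to Week 52. With equal rescue (10% or 30% in both arms) it barely moved: 1.70–1.83 against 1.74–1.83. Duration was not simulated.

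**5. Censoring dates.** Section 2.2.3.2 censors at the last CDAI assessment; 6.3.3.1 censors at the last visit or last contact. These differ whenever the last visit or contact has no CDAI, as at Week 56 in the SAP visit schedule.

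**The case against.** The strongest reply is that the general rule already governs. It reaches any remission or response assessment, 6.1.8 extends it to the ITT efficacy analyses, and these tables are ITT. The proportion endpoints in 2.2.2 and 2.2.3.1 are also written on CDAI thresholds without restating rescue, and nobody would read them as crediting it.

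For time to remission and time to response this largely stands. A reader might infer that the SAP counts a first remission reached on a rescue biologic as an event, so that one subject is a Week 26 failure in Table 14.2.1.1 and a remission event in Table 14.2.3.1.1. The documents do not support that: it would mean applying the general rule to one table and ignoring it for the other. For these two endpoints the gap is one of implementation.

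For duration the reply falls short, because the SAP gives an explicit formula with its own end date and the general rule provides no alternative. There is also some reason to expect literal programming. Section 6.1.5 makes discontinuations failures for the proportion endpoints, while 6.3.3.1 censors them here.

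Two further objections are fair. The rescue rule is not uniform: 2.2.1 is ordered in time and 6.1.8 is not, so ending duration at rescue follows the first reading and should be declared as such. And steroids are not settled. Section 6.1.8 lists systemic or rectal corticosteroids as rescue, but for worsening or an oral increase during taper it names failure only for the steroid-free analysis, and it allows use for reasons other than Crohn's disease. Treating every steroid increase as a breach of the rule would go beyond the text.

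**Conclusion.** The point holds for duration of remission and duration of response. Followed as written, 2.2.3.2 counts a remission or response kept after rescue as ongoing, which conflicts with 2.2.1 and 6.1.8. The individual discrepancy can be large (40.1 weeks censored against 6.1 weeks with an event), but that is one constructed subject.

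For time to remission and time to response, the intended classification can be inferred, but the event and censoring handling is not specified.

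A reader might infer that the gap flatters the active arm. The documents do not show this. Direction and size depend on rescue rates by arm, which they do not give. In the assumed cases with more rescue on placebo, crediting rescue weakens the treatment effect; with more rescue on active it would favour active; with equal rescue the time-to-remission comparison hardly changes. Nor is the primary or any key secondary test affected: SAP 6.3.3 makes these endpoints supportive and they lie outside the testing hierarchy in 6.1.2. The change should be made, but it is not critical to the trial's main claim.

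**What to change.** In SAP 2.2.3.2 and 6.3.3.1, before unblinding:

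1. State that duration of remission and of response ends, as an event, at the earlier of CDAI loss and the start of rescue as defined in 6.1.8. Say that this follows the time-ordered rule in 2.2.1, so a remission or response reached before rescue still counts.
2. State that a CDAI below 150, or a fall of at least 100, first recorded after rescue is not an event, and that the subject stays event-free to the censoring date. Do not censor at rescue: rescue signals new or unresolved disease, so that censoring would be informative.
3. Keep the CDAI-only derivation as a labelled supportive line.
4. Reconcile the censoring dates: last CDAI in 2.2.3.2, last visit or last contact in 6.3.3.1.
5. Reconcile within 6.1.8 whether a steroid increase during taper counts as rescue outside the steroid-free analysis. This is for the sponsor to settle, and the derivation should follow its answer.

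The cost is a few sentences and a rescue start date behind a flag that the primary endpoint already needs. Some durations become shorter. These are derivation rules only; nothing in the management of subjects changes.

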	 Assess whether subjects randomized to receive RHB-104 have a higher probability of being in a state of remission at the 16 week assessment as compared to subjects randomized to receive placebo 					
	5. Assess whether subjects randomized to receive RHB-104 have a higher probability of being in a state of steroid free remission at the 52 week assessment as compared to subjects randomized to receive placebo. Subjects must be maintained off steroids for 3 weeks in order to be determined to be in steroid free remission e.g. by week 49.					
	Selected Other Supportive Objectives					
	 To compare the arm-specific time to remission and response. 					
	To compare the arm-specific duration of remission and response.					
	To compare the proportion of subjects who have maintained remission from week 16 through week 52.					
	 Assess whether subjects randomized to receive RHB-104 have a higher probability of being in a state of response at the 16 week assessment as compared to subjects randomized to receive placebo. 					
	 To assess the difference between arms in health-related quality-of-life using the IBDQ and SF-36 questionnaire. 					
	 To compare arm-specific endoscopic 26-week changes using the CDEIS and SES-CD score in those subjects who consent to undergo colonoscopy 					
	To assess the effect of RHB-104 on markers of inflammation.					
	8. To assess the proportion of subjects in steroid free remission in each treatment arm at weeks 26. Subjects must be maintained off steroids for 3 weeks in order to be determined to be in steroid free remission e.g. by week 23					
	Other Exploratory Objectives					
	 To characterize the pharmacokinetic profiles of each of the active agents (and active metabolites for clarithromycin and rifabutin) using a population PK approach. 					

- To assess the efficacy outcome measures for interaction with the baseline assay results for MAP infection (positive versus negative) to use in development of MAP blood PCR testing.
- 11. To compare the arm-specific changes in MAP PCR status (positive to negative) from pre- to post-treatment at week 26 and week 52.
- 12. To compare arm-specific 26-week change from baseline in the endoscopic index (Δ CDEIS and Δ SES-CD) and the clinical index (Δ CDAI).
- 13. To compare the arm-specific changes in MAP culture status (positive to negative) from pre- to post-treatment at week 26 and week 52.

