2.1.3 Other Supportive Secondary Efficacy Objectives

1. To compare the arm-specific time to remission and time to response.
2. To compare the arm-specific duration of remission and duration of response.
3. To compare the proportion of subjects who have maintained remission from week 16 through week 52.
4. To assess whether subjects randomized to receive RHB-104 have a higher probability of being in a state of response at the 16 week assessment as compared to subjects randomized to receive placebo.
5. To assess the difference between the treatment groups in health-related quality-of-life using the IBDQ and SF-36 questionnaire instruments.
6. To compare arm-specific endoscopic 26-week changes using the CDEIS and SES-CD score in those subjects who consent to undergo colonoscopy.
7. To assess the effect of RHB-104 on markers of inflammation.
8. To assess the proportion of subjects in steroid free remission in each treatment arm at week 26. Subjects must be maintained off steroids for 3 weeks in order to be determined to be in steroid free remission e.g. by week 23.

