5. ANALYSIS POPULATIONS

All screened subjects who signed informed consent will be included in the disposition table counts.

The following populations will be used for data analysis.

The Intent-to-Treat (ITT) Population: The primary efficacy analyses will be based on the ITT population, which is defined as all subjects randomized. Subjects will be analyzed according to the treatment group to which they were randomized.

The Modified Intent-to-Treat (mITT) Population: The Modified Intent-to-treat population is defined as patients who fulfill all inclusion/exclusion criteria. The sensitivity analyses will be performed using the mITT population. Subjects will be analyzed according to the treatment group to which they were randomized.

The Safety Population (SAF): The safety population includes subjects who are randomized and receive at least one dose of study medication. The primary safety analyses will be based on the SAF population. Subjects will be analyzed according to the treatment which they actually received.

Per-Protocol Population (PP): The PP Population includes all randomized subjects who receive at least one dose of RHB-104 or placebo and complete dose escalation to target dose of 5 capsules bid, as well as all subjects without major protocol deviations that would have a significant impact on clinical outcome. Relevant protocol deviations may include errors in treatment assignment, the use of excluded medication that might affect study drug bioavailability, poor compliance (< 80% compliant over study duration), and subjects lost to follow-up. Protocol deviations will be reviewed and the list of major deviations warranting exclusion from the PP Population will be finalized prior to study unblinding. Subjects will be analyzed according to the treatment group to which they were randomized.

The primary and key secondary efficacy sensitivity analyses may be repeated on the PP Population.

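### The SAP gives two censoring rules for its time-to-event endpoints, and tests duration of remission and of response between arms only among subjects who achieved them

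*SAP*

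**What the plan says.** **Censoring.** SAP 2.2.3.2 ties censoring to the CDAI. Subjects who "continue to be in remission at the time of their last CDAI assessment will be censored at the date of their last CDAI assessment", and the wording for duration of response is parallel. For time to response: "For those subjects not experienced response, time to response will be censored at the date of the last assessment of CDAI score". The time-to-remission rule uses the same date but opens "For subjects still on study and not achieved remission at the time of" assessment, so it is limited to subjects who have not left the study. SAP 6.3.3.1 then gives a general rule for all four endpoints. Subjects without the event at study end are censored at their last recorded visit, and early discontinuers when they were last contacted. Neither section says which governs.

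**Durations.** The supportive objective in the protocol synopsis is "To compare the arm-specific duration of remission and response", and SAP 2.1.3 has the same aim: "To compare the arm-specific duration of remission and duration of response". SAP 2.2.3.2 restricts both quantities: "Duration of remission will be calculated only for patients achieving remission" and "Duration of response will be calculated only for patients achieved response". SAP 6.3.3.1 applies a Cox model with treatment and anti-TNF stratum, and a log-rank p-value, to all four endpoints, both durations included. The results go to Tables and Figures 14.2.3.1.2 and 14.2.3.1.4.

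**The concern.** Remission and response are defined only by CDAI. Time after the last CDAI therefore cannot contain an observed event, and a rule that counts it keeps subjects at risk when nothing can be recorded. This lowers the estimated event rate, and by more in an arm with more or longer unassessed follow-up. Two programmers, one following 2.2.3.2 and one following 6.3.3.1, would produce different analysis datasets.

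The durations raise a separate issue. Achieving remission or response happens after randomisation, and the trial is designed on the expectation that RHB-104 makes remission more frequent. The subjects entering the duration test are then not comparable between arms by randomisation. If RHB-104 brings into remission subjects who would not have remitted on placebo, and their remissions tend to be shorter or longer than average, the test can show a difference even when treatment does not change duration in anyone who would remit on either arm. The p-value could be read as randomised evidence on durability, which it is not.

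**Working it through.** The plan gives no sample size, duration, relapse or dropout figure for these endpoints, so there is no stated figure to reproduce. The inputs from the documents are the visit schedule (SAP 4.1.1), the design remission rates of 36% and 21%, and 162 subjects per arm (SAP 6.1.9).

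**1. Censoring rules side by side**

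| Endpoint | 2.2.3.2 | 6.3.3.1, no event at study end | 6.3.3.1, early discontinuation |
|---|---|---|---|
| Time to remission | last CDAI, only if still on study | last visit | last contact |
| Duration of remission | last CDAI | last visit | last contact |
| Time to response | last CDAI | last visit | last contact |
| Duration of response | last CDAI | last visit | last contact |

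The schedule has CDAI at week 52 and none at week 56. For completers the gap is 56 − 52 = 4 weeks. Each visit has a ±7-day window, so it can range from 4 − 2 = 2 to 4 + 2 = 6 weeks. For discontinuers it has no upper limit.

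The effect on the log-rank test was simulated with 162 per arm. Relapse was exponential with mean 26 weeks and seen at the next CDAI visit. Dropout was uniform over weeks 0 to 52, with last contact a fixed lag later, capped at week 56. Relapse time, dropout and lag are assumptions. Cells show the 95th percentile of the absolute change in z, then the share of trials in which significance changed (1,500 trials; 1,000 for the last column).

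| Dropout by arm, contact lag | Duration | Time to event, onset weeks 8–26 | Time to event, onset weeks 8–52 |
|---|---|---|---|
| none | 0.22; 1.0–1.2% | 0.00; 0.0% | 0.16; 1.4% |
| 20%/20%, 4 weeks | 0.28; 1.6% | 0.07; 0.7% | 0.17; 1.5% |
| 30%/10% or 10%/30%, 8 weeks | 0.49–0.53; 2.3–3.1% | 0.27–0.28; 1.9–4.7% | 0.39–0.42; 6.1–6.4% |

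**2. Duration among achievers**

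Using the week 26 design rates for ever remitting, the test would include 162 × 0.21 = 34.0 placebo and 162 × 0.36 = 58.3 RHB-104 subjects, about 92 of 324 (28%). Ever-remission rates can only be higher than the week 26 rates.

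To see the mechanism, assume that 21% remit on either arm with mean duration 26 weeks regardless of treatment. A further 36% − 21% = 15% remit only on RHB-104, with mean duration m. Durations are exponential and observed for at most 30 weeks. The observed mean for a group with mean m is m(1 − e^(−30/m)). For m = 26 this is 26 × (1 − 0.3154) = 17.8 weeks, the placebo figure. The RHB-104 figure is (0.21 × 17.8 + 0.15 × extra-remitter mean) / 0.36. For m = 10 the extra mean is 9.5, giving (3.74 + 1.43) / 0.36 = 14.3 weeks. The last two columns are the share of 4,000 simulated trials per row with |z| > 1.96.

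| m, extra remitters (weeks) | Observed mean, RHB-104 remitters | RHB-104 called worse | RHB-104 called better |
|---|---|---|---|
| 10 | 14.3 | 28.4% | 0.05% |
| 15 | 15.8 | 13.4% | 0.3% |
| 20 | 16.9 | 5.2% | 1.4% |
| 26 | 17.8 | 2.2% | 3.0% |
| 40 | 19.2 | 0.5% | 10.4% |

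A separate run used a median of 20 weeks for those remitting on either arm, 26 weeks of follow-up and 2,000 trials. It gave the same picture: 45% and 18% rejections, almost all favouring placebo, when the extra remitters' median was 5 and 10 weeks; 5.6% at 20 weeks; and 17% and 34%, all or almost all favouring RHB-104, at 40 and 80 weeks. When the extra remitters resemble the others, the test keeps about its nominal 5%.

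**The case against.** The best case for the plan has four parts.

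- **Status.** SAP 6.3.3 calls tests in this family descriptive or supportive, and the end of SAP 6.1.2 treats p-values outside the hierarchy as nominal. This stands and limits the weight of the point.
- **Disclosure.** The restriction to achievers is stated openly, and duration given remission is a well-defined quantity. If added remitters have short remissions, a shorter average among RHB-104 remitters is a true description. That supports describing the durations by arm. It does not support a between-arm hazard ratio and p-value.
- **Durability is tested elsewhere.** Durable remission from week 26 to week 52 is fourth in the hierarchy, and sustained remission from week 16 to week 52 is supportive; both count all randomised subjects (SAP 2.2.2, 2.2.3.1, 6.3.2.3, 6.3.3.2). This stands for remission. Response has no counterpart: it is tested at weeks 16, 26 and 52 only, and SAP 6.3.3.3 pools sustained and late responders at week 52.
- **Size.** Every magnitude above rests on assumed durations, dropout and contact lag. This also stands.

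Three stronger readings are tempting. A reader might infer that the Intent-to-Treat titles on the duration outputs contradict Section 5, where "The primary efficacy analyses will be based on the ITT population, which is defined as all subjects randomized". But that sentence concerns the primary analyses, and the SAP puts the same label on the CDEIS and SES-CD tables, which cover only subjects who consented to colonoscopy (6.3.3.10). The label evidently names the source population. A reader might also infer that 6.3.3.1 presents a significant duration test as a treatment effect on duration. Its interpretive sentences describe time to first event and fit the durations poorly, so they are weak evidence of that. Finally, the censoring rules do not conflict for every subject on every endpoint: for time to remission, early discontinuers fall under 6.3.3.1 alone, which is a gap in 2.2.3.2.

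**Conclusion.** The point holds at minor to moderate weight.

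The censoring rules are wrong as written: 2.2.3.2 and 6.3.3.1 give different dates, and the 6.3.3.1 dates include follow-up in which the event cannot be observed. The numerical effect is expected to be small. In the illustrations, significance changed in 0 to 1.4% of trials without dropout, and in up to 6.4% with strongly unequal dropout and an 8-week contact lag. The actual dropout is not in the documents.

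The tests of duration among achievers are not randomised comparisons. They can mislead in either direction, and the documents determine neither the direction nor the amount. The simulated rates show what is possible under stated assumptions and do not predict this trial. They do not support a claim that the test is biased for or against RHB-104.

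Neither part touches the primary or key secondary conclusions.

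**What to change.** 1. In SAP 6.3.3.1, censor all four endpoints at the date of the last CDAI assessment, in place of the last visit and last contact. In SAP 2.2.3.2, extend the time-to-remission rule to subjects who discontinued.
2. Report duration of remission and of response among achievers by arm with Kaplan-Meier estimates, without a hazard ratio or p-value. Title or footnote Tables and Figures 14.2.3.1.2 and 14.2.3.1.4 as covering subjects achieving remission or subjects achieving response. Time to remission and time to response keep their planned tests in all randomised subjects.

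The cost is a few SAP sentences and four output titles. No new data or new endpoint is needed. SAP 6.8 provides for such changes before unblinding.

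The downside is that the objective of comparing durations is then answered descriptively. Between-arm inference on durability of remission rests on the planned durable and sustained remission endpoints. Durability of response would have no between-arm test, and the SAP should say so.
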